4. STUDY POPULATION

4.1 Population (base)

Patients suffering from sciatica that visit the general practitioner (GP collective Haarlemmermeer (60 GP) and Kennemerland (125 GP) referring to the Spaarne Gasthuis location Haarlem and location Hoofddorp (adherence 750.000 patients) are evaluated to be candidates for this study. If the general practitioner diagnoses a lumbar radicular syndrome (LRS) (sciatica) with an NRS leg pain of 6 points or more on a 10 points scale, and the duration of pain is longer than 3 weeks and shorter than 8 weeks, the patients are offered to participate in the RCT. If they are willing to consider participating in the RCT, the GP will send the contact details to the study investigator. Patients will be offered at least 48 hours to decide whether they want to be enrolled in the study. The study investigator will contact the patients and explain the study again. If patients are deciding to cooperate, informed consent will be signed. If patients are randomized to continue usual care, the GP will be informed and he/she will conduct conservative treatment as deemed suitable. If the patient is randomized to TEI, the patient is referred to the anaesthesiologist to receive TEI. TEI treatment will be received within 4 days.

4.2 Inclusion criteria

In order to be eligible to participate in this study, a subject must meet all of the following criteria:

- Sciatica;
- Leg pain of 6 or more on a 10 point NRS (Numeric Rating Scale) scale with a duration of >3 and <8 weeks;
- Patient is willing to accept the possible costs for the treatment by the pain physician
- Informed consent.

4.3 Exclusion criteria

A potential subject who meets any of the following criteria will be excluded from participation in this study:

- Age under 18 years;
- Condition preventing to receive TEI (for instance, allergy for lidocaine);
- Severe scoliosis;
- TEI received in 6 months before randomization date;
- Surgery for sciatica at the same level;
- Surgery for sciatica at another level within one year before inclusion;

- Pregnancy.

4.4 Sample size calculation

We hypothesize that patients in the intervention group will have a mean NRS for leg pain of 4.0 on a 10-point scale at two weeks after treatment with TEI and patients in the control group will have a mean NRS for leg pain of 5.5 two weeks after randomization. A difference of 1.5 points on the NRS scale will be considered clinically relevant [17]. With a standard deviation of 2.6 (according to results of Joswig [18]), a power of 90% and a level of significance of 5% 64 patients are needed per group. This is a total of 128 patients. With a loss to follow-up of 10% we aim to include 142 patients.

5. TREATMENT OF SUBJECTS

5.1 Investigational product/treatment

Patients are referred to the anaesthesiologist to receive TEI within 4 days after randomization.

For injections below L3, where the space around the nerve root is larger and thus dilution of the injectable is more than in the area around the nerve root in the higher lumbar area (above L3), the dosage of the medication will be higher.

For injections at L3 or below :1,5 ml lidocaine 2% and 40mg methylprednisolone acetate is injected transforaminally in close proximity of the nerve root, according to usual care

For injections above L3: 1,5 ml lidocaine 1% and 10mg dexamethasone is injected transforaminally in close proximity of the nerve root, according to usual care.

Administration of the injection will be performed in an outpatient clinic setting and will take 15 minutes. After the procedure, the patient will stay at the recovery room for 30 minutes for monitoring.

5.2 Use of co-intervention

Oral pain reducing medication according to usual care is allowed. This is prescribed, if necessary, by the GP. Since it is a randomized controlled trial, it is reasonable to expect that participants in both treatment arms will demonstrate comparable variation in oral pain medication.

5.3 Escape medication

N.a.

6. METHODS

6.1 Study parameters/endpoints

6.1.1 Main study parameter/endpoint

NRS leg pain: The pain intensity in the leg and the back will be measured with a 10-point horizontal Numeric Rating Scale (NRS), ranging from 0 (no pain) to 10 (worst imaginable pain). During each visit the NRS leg pain and NRS back pain will be scored. The patient is not entitled to see the pain scores indicated during previous visit(s). The NRS scores will be measured at baseline and at 1, 2, 4, 10 and 21 weeks after randomization.

The average score for NRS leg pain at two weeks after injection is compared to the average score for NRS leg pain in the prolonged conservative care group, 2 weeks after randomization. This will be calculated again at 4 weeks after randomization.

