Sponsor	The sponsor is the party that commissions the organisation or performance of the research, for example a pharmaceutical company, academic hospital, scientific organisation or investigator. A party that provides funding for a study but does not commission it is not regarded as the sponsor, but referred to as a subsidising party.
TEI	Transforaminal Epidural Injection
TEIAS	Transforaminal Epidural Injection in Acute Sciatica
VAS	Visual Analogue Scale
WMO	Medical Research Involving Human Subjects Act; in Dutch: Wet Medisch-wetenschappelijk Onderzoek met Mensen

SUMMARY

Rationale: To study (cost) effectiveness of the transforaminal epidural injection with analgesic and anti-inflammatory medication (TEI) in order to relieve the symptoms and to evaluate the intervention as a predictor tool for symptoms of sciatica in the long term.

Objective: To evaluate the percentage of patients that experience satisfactory (long term) decrease in leg pain in the TEI group in comparison to the conservative care group.

Study design: Randomised controlled trial

Study population: Patients that suffer 3-8 weeks from sciatica (Numeric Rating Scale ≥ 6 , on a 10 point scale)

Intervention: transforaminal epidural injection with analgesic and anti-inflammatory medication

Main study parameters/endpoints: the percentage of patients that experience satisfactory decrease (NRS lower than 4) in leg pain after 2, 10 and 21 weeks after randomization in both treatment arms

Nature and extent of the burden and risks associated with participation, benefit and group relatedness: the participants fill in questionnaires at baseline, at 1, 2, 4, 10 and 21 weeks after randomization. Participants will also fill in cost-diaries during this period. TEI as an intervention tool is considered usual care for sciatica patients, though the timing of the injection is not clearly defined. The extent of risk from TEI is comparable to usual care.

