2. OBJECTIVES

Primary study objective:

To study effectivity of the epidural injection with analgesic and anti-inflammatory medication to relieve the symptoms within two weeks follow up.

It will be evaluated what the average leg pain score is in both treatment arms at two weeks follow up. It will be evaluated how long the effect lasts.

The leg pain and functionality at 4 weeks after randomization will also be evaluated to get informed on the responsiveness on TEI in a somewhat later stage.

Secondary study objectives:

To evaluate the outcome of TEI in the first two weeks after randomization as a predictor of NRS leg pain at 14-16 and ca 26 weeks after onset of leg pain.

Ideally, responsiveness to TEI can predict the clinical condition at 14-16 weeks after onset of sciatica. The hypothesis is that being non-responsive to TEI within two weeks, predicts an unsatisfactory condition after 14-16 weeks of suffering. This is the category of patients that in contemporary care in the Netherlands will be offered a surgical intervention. If our hypothesis is correct, in the future, this population of patients can be offered a surgical intervention at an earlier time point.

The ca 26-week time point is chosen since in the Sciatica trial [2], both the conservative and the surgical group demonstrated comparable outcome data.

Patients in this study are included while suffering from severe leg pain for 3-8 weeks.

Presumably most patients will enter the study with 4-6 weeks of leg pain. This means that on average 10 weeks after randomization, the 14-16 week leg pain time point is reached. This means that 21 weeks after randomization the ca 26-week leg pain time point is reached.

The response in NRS leg pain, ODI and patient satisfaction at 1 week after injection and at 2 weeks after injection will be correlated to the value of these parameters at 10 and 21 weeks after randomisation.

To evaluate the cost-effectivity of analgesic/anti-inflammatory epidural injections to relieve symptoms of early sciatica.

A substantial portion of the patients in this study will eventually have an MRI of the lumbar spine. These MRIs will be evaluated according to our standard MRI evaluation protocol, that has been proven to generate additional successful conclusions and subsequent publications in the past [10-15]. Protruding disc, disc and vertebral end plate changes (MODIC) will be correlated to clinical data.

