NRS leg pain that decreases below the value of 4 (on a 10 point scale) within two weeks after TEI is documented as successful effect of TEI. NRS leg pain that remains higher than a value of 4 at a time interval of two weeks after TEI makes a patient eligible for surgery if the patient requests for surgery. If surgery is requested by the patient (either in the control or intervention group), general guidelines for timing of surgery will be conducted, meaning that the patient is encouraged to postpone surgery till 14-16 weeks after onset of pain. This decision is made using Shared Decision Making and it is possible that the patient is operated before the 14-16 week time point. The patients who are randomized cannot be operated in the first two weeks after randomization, unless sudden loss of strength or a cauda equina syndrome is reported. We expect that during these two weeks TEI will have its effect. Four

weeks after randomization the outcome parameters are measured again to be informed on the late effect of TEI. Patients will be followed up for a total duration of 21 weeks starting from the moment of randomization. Questionnaires will be filled in at baseline, 1, 2, 4, 10 and 21 weeks follow-up. A schematic overview of the study procedures is outlined in figure 1. Note that this figure does not hold into account that it is possible for patients randomized to the treatment group to receive additional injections if necessary.

[figure not shown]

Fig.1 Flow diagram of study procedures

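### The primary comparison is timed from injection in the TEI arm but from randomisation in controls, which contradicts the assessment schedule and fits poorly with intention-to-treat

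*Combined protocol and SAP*

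**What the plan says.** **Split clock.** Section 6.1.1 describes the primary comparison, on the TEI side, with these words: "The average score for NRS leg pain at two weeks after injection is compared to the average score for NRS leg pain". For controls it then switches clock, to the score of the "prolonged conservative care group, 2 weeks after randomization". Section 4.4 repeats the split: its TEI mean of 4.0 is dated from the injection, whereas controls "will have a mean NRS for leg pain of 5.5 two weeks after randomization".

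**Randomisation clock.**
- The first paragraph of 6.1.1: "The NRS scores will be measured at baseline and at 1, 2, 4, 10 and 21 weeks after randomization". The 4-week repeat in the same section is also timed from randomisation.
- The Summary counts weeks from randomisation in both arms, although its endpoint is the percentage with NRS below 4 and not a mean.
- Section 3: "Patients will be followed up for a total duration of 21 weeks starting from the moment of randomization".
- Section 6.3 applies one questionnaire schedule to both arms and places the primary endpoint 2 weeks after randomisation.
- The first sentence of 8.2 measures the decline in NRS leg pain to 2 weeks after randomisation.

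**Clock not settled.**
- Section 2 asks "what the average leg pain score is in both treatment arms at two weeks follow up", without saying from when.
- Section 8.1 specifies intention-to-treat and an unpaired t-test. It implies week 2 through its 4-week repeat but states no time origin.
- The perceived-recovery sentence in 8.2 allows either randomisation or injection.

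**The concern.** A randomised comparison needs the same assessment time in both arms, and that time must exist for every randomised patient. The stated definition fails on both counts.

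First, TEI is given within 4 days after randomisation (sections 3 and 5.1). Two weeks after injection is therefore day 14 to 18 after randomisation, against day 14 for controls. Section 3 itself says that sciatica resolves without intervention in a significant share of patients, so extra elapsed time in one arm would tend to count as a treatment effect.

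Second, a patient allocated to TEI who is never injected has no score two weeks after injection. Section 6.5 classes those who refuse TEI as cross-overs, section 6.6 keeps patients withdrawn from treatment in follow-up, and 8.1 calls for intention-to-treat. The literal endpoint is undefined for such patients, in one arm only.

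The trial is open-label and 8.1 does not settle the matter, so the choice of clock for the primary endpoint could be left until the data are in hand.

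**Working it through.** **1. The plan's own sample size (4.4).** Inputs: difference 5.5 − 4.0 = 1.5, SD 2.6, power 90%, significance level 5% (taken as two-sided), 1:1 allocation.

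n per group = 2 × (1.960 + 1.282)² × 2.6² / 1.5² = 63.1, so 64. The exact t-test power at 64 per group is 89.9%. Allowing for loss to follow-up, 128 / 0.90 = 142.2, against the stated 142. The arithmetic reproduces; the point concerns the endpoint definition only.

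**2. Assessment day, counted from randomisation.**

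| Reading | TEI arm | Control arm | TEI-arm patient never injected |
|---|---|---|---|
| Scheduled week-2 score | day 14 | day 14 | has a score |
| 6.1.1 taken literally, injection on day 0–4 | day 14–18 | day 14 | no score |

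**3. Size under the literal reading.** The documents give no baseline mean, no control-arm recovery curve and no distribution of injection delays, so the following is an illustration. Assumptions: baseline mean B of 6, 7 or 8 (entry requires at least 6); a mean of 5.5 on day 14 (the 4.4 control value); no true treatment effect; and the same lag for every TEI patient.

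- Standard error = 2.6 × √(2/64) = 0.460. Rejection rates come from the two-sided noncentral t with 126 degrees of freedom, at nominal 5%.
- Linear recovery: bias = (B − 5.5)/14 × lag. Example: (8 − 5.5)/14 × 4 = 0.714.
- Recovery flattening to a plateau P: k = ln[(B − P)/(5.5 − P)]/14 and bias = (5.5 − P) × (1 − e^(−k × lag)). Example with B = 8 and P = 4: k = ln(4/1.5)/14 = 0.0701, and the 4-day bias is 1.5 × (1 − e^(−0.280)) = 0.367.

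Bias in NRS points favouring TEI, for B = 6 / 7 / 8:

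| Lag | Linear | Plateau 4 | Plateau 5 |
|---|---|---|---|
| 1 day | 0.036 / 0.107 / 0.179 | 0.031 / 0.072 / 0.101 | 0.024 / 0.047 / 0.060 |
| 2 days | 0.071 / 0.214 / 0.357 | 0.060 / 0.141 / 0.196 | 0.047 / 0.090 / 0.113 |
| 4 days | 0.143 / 0.429 / 0.714 | 0.118 / 0.269 / 0.367 | 0.090 / 0.164 / 0.200 |

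Rejection rates over all these cases are 5.0–6.7% for a 1-day lag, 5.1–12.0% for 2 days and 5.4–33.8% for 4 days. As a share of the 1.5-point target, the 2-day bias runs from 0.047/1.5 = 3% to 0.357/1.5 = 24%.

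The 33.8% needs a baseline mean of 8, linear recovery continuing past day 14 and every injection on day 4. With a plateau of 4 or 5, the highest 4-day rejection rate is 12.4% or 7.2%. If controls are flat after day 14, the bias is zero.

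**The case against.** The strongest reply is that nobody would analyse the trial this way. Both arms complete the same questionnaires from randomisation, section 6.3 names the primary endpoint on that clock, and section 3 expects TEI to act within the first two weeks after randomisation. Patients withdrawn from treatment stay in follow-up and so have a scheduled week-2 score. On that view this is a wording slip with no effect on the result. Most of this stands: the scheduled score is the probable choice, and uninjected patients are lost only if the 6.1.1 sentence is followed to the letter.

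The injection clock cannot simply be dismissed, however. Section 2 plans to use responses at 1 and 2 weeks after injection, section 3 defines success within two weeks after TEI, and 6.1.3 lists leg pain after injection among the TEI data. That last item has no stated timing, so it does not establish that a score two weeks after injection will be collected. These passages show that both readings have some support, which is a reason to settle the point.

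The illustration is also open to challenge. It models bias in TEI's favour only. Section 1 says that pain can return hours, days or weeks after an injection, so later assessment could work against TEI. The one trajectory reported there is roughly flat over 14 days, but it comes from injected patients and is not a control curve. The figures show a possible size and are not a forecast.

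**Conclusion.** The concern holds and should be fixed. Sections 6.1.1 and 4.4 state a primary comparison with different time origins in the two arms. That conflicts with the NRS schedule, section 6.3 and the first sentence of 8.2, and 8.1 does not resolve it.

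The contradiction and the missing value for uninjected TEI-arm patients follow from the text alone and rest on no assumption. In the probable case, the scheduled week-2 score in both arms, the timing bias is zero; the comparison is fair but is not the endpoint that 6.1.1 and 4.4 describe. Only the literal reading brings bias. Its size cannot be derived from the documents and depends entirely on the assumed baseline means, recovery shapes and lags shown above.

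**What to change.** - In 6.1.1, 4.4 and 8.1, define the primary endpoint as NRS leg pain at 2 weeks after randomisation, with the same window in both arms, for all randomised patients whether or not injected.
- Restate the hypothesis of 4.0 versus 5.5 on that clock.
- In 8.2, remove the injection alternative from the between-arm comparison of perceived recovery.
- Scores timed from injection can stay for descriptive or predictive analyses within the TEI arm, as sections 2 and 3 envisage. Nothing here bears on eligibility for surgery.

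The cost is a few sentences. The questionnaire schedule is unchanged, and 64 per group still stands if 1.5 points and SD 2.6 are kept. The downside is that, with injection on day 0 to 4, TEI patients are assessed 10 to 14 days after injection and not always at a full 14. The sponsor should confirm that the 4.0 assumption is still reasonable at that interval.

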6.1.2 Secondary study parameters/endpoints

Sciatica is not only characterized by pain in the leg, but also by discomfort in functioning. Therefore the following parameters will also be evaluated.

NRS back pain: The pain intensity in the leg and the back will be measured with a 10-point horizontal Numeric Rating Scale (NRS), ranging from 0 (no pain) to 10 (worst imaginable pain). During each visit the NRS leg pain and NRS back pain will be scored. The patient is not entitled to see the pain scores indicated during previous visit(s). The NRS scores will be measured at baseline and at 1, 2, 4, 10 and 21 weeks after randomization.

Oswestry Disability Index (ODI): The functionality of the patient with a focus on walking and daily activities will be measured with the Oswestry Disability Index that is usually measured for sciatica complaints. The scale ranges from 0 (no disability) to 50 (worst disability possible). During each visit the ODI will be scored. The patient is not entitled to see the scores indicated during previous visit(s). The ODI scores will be measured at baseline and at 1, 2, 4, 10 and 21 weeks after randomization.

EuroQoL (EQ-5D): The EuroQoL (five point EQ-5D) will be used for the cost utility analysis. The tool measures five dimensions: mobility, self-care, daily activities, pain/discomfort, and anxiety/depression. Each dimension consists of one item, while three levels are distinguished (no problems, some problems, many problems). Use of the EuroQoL needs to be registered

(euroqol.org). The EuroQol scores will be measured at baseline and at 2, 10 and 21 weeks after randomization.

Quality of Life VAS (Health state utility VAS): To represent the patients perspective, utility will also be estimated using a VAS for the valuation of the patient's health state (ranging from 0 = as bad as death to 100 = perfect health), measured at baseline and at 2, 10 and 21 weeks after randomization.

Likert perceived recovery patient: To measure the perceived recovery a seven-point Likert scale will be used. The score on this scale varies from 'completely recovered' to 'worse than ever'. The Likert scores will be measured at baseline and at 1, 2, 4, 10 and 21 weeks after randomization.

Costs (Cost intervention, health care use, and loss of productivity): Cost diaries will be filled out at 10 and 21 weeks after randomisation. Health care utilization (including physiotherapy, visits to GP and specialists, nursing care and medication), patient costs, and absenteeism will be measured using cost diaries filled out by the patient.

Complications: Post-TEI exacerbation of NRS leg pain (>1 point additional leg pain) that lasts for at least 24 hours will be documented as a clinically relevant complication of TEI. Other rare adverse events from treatment with TEI such as pain at site of injection, persisting numbness, vasovagal reaction, accidental discal puncture, accidental dural puncture or headache will be recorded as well.

Radiological parameters: the level of disc herniation, the size and shape of disc herniation, disc degeneration (Pfirrmann scale), vertebral end plate changes, and facet degeneration (Weishaupt scale) will be evaluated by two independent researchers, blinded to clinical and histological data, on T2 weighted sagittal and transversal MRI.

Histology: During surgery, the herniated disc material will be collected and fixed in 4% formaldehyde solution. For evaluation, the tissue will be subsequently embedded in paraffin blocks. These blocks will be stained with Hematoxylin and used for general macrophage staining (CD68), and subtype macrophage staining: M1(iNOS & CD40) and M2 (Arg1 & CD163), T cell staining (CD45-RO) and B cell staining (CD20). Furthermore, presence of Propionibacterium Acnes and Staphylococcus Epidermidis will be verified by PCR analysis for 16S rDNA. Positive samples will be gram stained for further identification of the bacteria.

All histological data will be quantified by two independent researchers, blinded to clinical and MRI data, and an inter-agreement analysis will be conducted.

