3. STUDY DESIGN

This is a prospective, open-label, randomized controlled trial on patients suffering from acute sciatica (3-8 weeks pain in the leg with a NRS ≥ 6) (see inclusion and exclusion criteria) in which consecutive patients who meet the inclusion criteria are invited to participate in the trial. The trial will take place at the Spaarne Gasthuis Hospital (SG) in Hoofddorp and Haarlem, the Netherlands in cooperation with researchers from Leiden University Medical Center (LUMC), Leiden, the Netherlands. Patient recruitment will occur at GP practices (GP collective Haarlemmermeer and Kennemerland, 185 GP's). The GP will diagnose the patient and, if the patient is diagnosed with sciatica, refer to the study investigator.

Eligible patients that are willing to participate are randomized to treatment with transforaminal epidural injections (treatment group) or standard conservative care (control group).

Randomization will take place using block randomization in a 1:1 allocation ratio. Patients from the treatment group will be treated with TEI, oral pain medication and, if deemed necessary by the GP, physiotherapy. The control group will only receive oral pain medication and if deemed necessary additional physiotherapy. For this study, the control group will not include placebo injections since we want to compare treatment with injections to treatment without injections. The focus will not be on the type of medication that is contained in the injection. Furthermore, a control group without injections will demonstrate what percentage of patients will experience spontaneous relief of symptoms (only using medication and/or physiotherapy) as it is known that in a significant part of the patients sciatica resolves without any intervention.

At baseline, clinical and demographic data are gathered for patients in both groups. Patients from the treatment group will receive TEI within 4 days after randomization. Patients from this group can receive multiple injections but an injection is only repeated after a certain interval time according to usual anaesthesiological guidelines. For all injections, details on timing, frequency and prevailing complications will be gathered.

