6.1.3 Other study parameters

Data with respect to the following variables will be collected at baseline:

- Demographic data;
- Age, gender, length, weight, BMI, tobacco exposure, alcohol abuse;
- History of previous radicular symptoms in the legs;
- Usage of pain medication.

Data with respect to the following items will be collected concerning TEI:

- Timing of administration (days after randomization);
- Number of injections and timing of those;
- NRS leg pain after injection;
- Other complications.

Data during follow up will be collected:

- If an MRI is performed: MRI data;
- If surgery is performed: disc material for histology.

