10. ADMINISTRATIVE ASPECTS, MONITORING AND PUBLICATION

10.1 Handling and storage of data and documents

Data will be collected using Castor EDC (web based secured system provided by LUMC). Baseline data will be collected during inclusion of the participant and directly registered in Castor by a researcher from the LUMC. Data on TEI, MRI and lumbar surgery will be collected from the electronic patient system Epic in Spaarne Gasthuis by the treating physician and by a researcher from the LUMC and processed in Castor. Specific data on the TEI procedure will be filled in on a paper CRF by the anaesthesiologist and subsequently processed by a researcher from the LUMC in Castor. Other data will be collected at predefined follow-up moments through digital questionnaires that the participants will fill in at home. These will be processed automatically in Castor. Castor EDC will code the patient data into untraceable ID's. All data will be safeguarded and stored for 15 years after the study is finished. All data will be handled according to the guidelines of GRP. This obligates all researchers to comply to the quality assurance standards, which include monitoring, risk assessment, privacy of patient data, and transparency of information to the patient. The LUMC will be responsible for the processing of data.

In order to warrant privacy patient data and disc material will be coded. Only with the key data can be traced back to a specific individual. The key is securely saved at the local research site and only the principal investigator, research monitor and Healthcare and Youth Inspection (Inspectie Gezondheidszorg en Jeugd) will have access to the key. No traceable data will be published. Patients will give permission for these authorities to access the key and their personal data through the informed consent. At any moment patients can withdraw their permission. Data collected before withdrawal of consent will be used. If disc material has been collected, it will be destroyed after withdrawal of consent. Analyses of disc material performed before withdrawal of consent will be used.

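### The one TEI complication with a numeric definition cannot be met from a pre-injection score of 9 or 10, and the scores and duration item it needs are not specified

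*Combined protocol and SAP*

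**What the plan says.** - **Definition.** Section 6.1.2 (Complications): "Post-TEI exacerbation of NRS leg pain (>1 point additional leg pain) that lasts for at least 24 hours will be documented". The section classes such an event as clinically relevant. It names further TEI events for recording, without a numeric threshold.
- **Scale.** Section 6.1.1 describes the NRS as "ranging from 0 (no pain) to 10 (worst imaginable pain".
- **Entry.** Section 4.2 requires "Leg pain of 6 or more on a 10 point NRS (Numeric Rating Scale) scale", so 9 and 10 are eligible scores.
- **Scheduled scores.** Section 6.1.1: "The NRS scores will be measured at baseline and at 1, 2, 4, 10 and 21 weeks after randomization". None of these is tied to the date of injection.
- **Timing of the injection.** Section 3: "Patients from the treatment group will receive TEI within 4 days after randomization". Repeat injections are permitted.
- **TEI data items.** Section 6.1.3 lists "NRS leg pain after injection", with no time after injection, followed by other complications. It lists no score before injection. Section 10.1 adds: "Specific data on the TEI procedure will be filled in on a paper CRF by the anaesthesiologist". The contents of that form are not given.
- **Wider safety capture.** Section 3 plans to gather timing, frequency and complications for all injections. Section 7.2.1 records every adverse event that the patient volunteers or that the investigator or staff observe, with no NRS threshold. It also gives a literature rate of 2.4% for transient exacerbation of pain.

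**The concern.** The rule needs three things: room on the scale for a rise of more than 1 point, a before-and-after pair of scores tied to the injection, and evidence that the rise lasted 24 hours.

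The first is absent at the top of the scale. Two patients with similar worsening would be classified differently only because one started at 7 and the other at 9. The second and third are not specified, so a flare of one to three days can begin and end before the next scheduled score.

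What is at stake is the count of a complication that the protocol itself calls clinically relevant, in an open-label trial without a data safety monitoring board (section 11.2). The effect of the ceiling on that count can only be downward, and short flares that go unseen push it the same way.

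**Working it through.** **1. Ceiling.** Inputs: scale maximum 10 (section 6.1.1), entry at 6 or more (section 4.2), rise of more than 1 required (section 6.1.2). Largest possible rise = 10 − score before injection.

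| Score before injection | Largest rise | More than 1 possible? |
|---|---|---|
| 6 | 4 | yes |
| 7 | 3 | yes |
| 8 | 2 | yes, in whole numbers only by reaching 10 |
| 9 | 1 | no |
| 10 | 0 | no |

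Two of the five eligible whole-number scores cannot register the event. This step needs no assumption, apart from noting that the relevant score is the one at injection, which may differ from the entry score.

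**2. Timing.** For a first injection on day 0 to 4 after randomisation, the week-1 score (day 7) falls 7 − 4 = 3 to 7 − 0 = 7 days later. A flare of 24 to 72 hours can be over by then. For a repeat injection the gap is not bounded in this way: between the week-4 and week-10 scores it could approach 10 − 4 = 6 weeks.

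**3. Reference score.** Baseline could serve for the first injection, but its distance from the injection is not fixed: section 6.3 describes the baseline visit after randomisation, while section 10.1 places baseline collection during inclusion. Baseline cannot serve for a repeat injection.

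**4. Size of the TEI arm.** The plan's sample size reproduces. With SD 2.6, difference 1.5, power 90% and two-sided 5%, n = 2 × [2.6 × (1.960 + 1.282) / 1.5]² = 63.1, so 64 per group and 128 in total. Then 128 / 0.9 = 142.2, against the stated 142. At 1:1 allocation the TEI arm is 142 / 2 = 71.

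**5. Illustrative loss from the ceiling.** The documents give no baseline distribution. Assumption: a normal score rounded to whole numbers, cut at 6 or more, with values above 10 counted as 10. Further assumptions: the 2.4% of section 7.2.1 applies to this definition, it does not depend on the starting score, and there is one injection per patient. Expected events without a ceiling = 0.024 × 71 = 1.70. Loss = 1.70 × share at 9-10.

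| Underlying mean | SD | Share at 9-10 | Patients of 71 | Expected events lost |
|---|---|---|---|---|
| 7 | 1.0 | 7% | 5 | 0.12 |
| 7 | 1.5 | 19% | 13 | 0.32 |
| 7.5 | 1.0 | 16% | 12 | 0.28 |
| 7.5 | 1.5 | 28% | 20 | 0.47 |
| 8 | 1.0 | 31% | 22 | 0.53 |
| 8 | 1.5 | 39% | 28 | 0.66 |

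The chance of registering no event at all is (1 − 0.024)^71 = 18% without a ceiling. With 39% of patients at 9-10 it is about 35%. The loss from unseen short flares (step 2) comes on top and cannot be quantified from the documents.

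**The case against.** A reader might infer that harm from the injection will be under-counted. The documents do not support that. Section 3 plans to gather complications for every injection, repeats included. Section 6.1.3 does list a post-injection NRS directly before other complications, which suggests that it is meant to capture this event. Section 7.2.1 records adverse events without a threshold, whether volunteered or observed, and specifically includes leg pain from TEI that leads to hospitalisation or disability. The recovery scale at week 1 also extends to worsening. A patient at 9 or 10 who gets worse can be recorded by these routes. This part of the objection stands, and it confines the point to one threshold-defined complication.

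It is also fair to say that a pre-injection score is unspecified rather than shown to be absent, because the contents of the TEI form are not given. Nor should a reader infer that the trial will set its rate against the 2.4%: section 7.2.1 gives that figure as background, and section 8 plans no analysis of complication rates.

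The expected loss from the ceiling is below one event under every assumption tabulated, and the trial could not estimate this rate precisely in any case: exact 95% intervals for 1/71 (0.04% to 7.6%) and 2/71 (0.3% to 9.8%) largely overlap. That stands and limits the severity. An out-of-date reference score can err in either direction, so a downward bias from that source is not shown at scores of 6 to 8. Finally, 10 is anchored as the worst pain imaginable, so the ceiling is partly a property of the scale. That does not help the patient at 9, who has room to worsen but not by enough to count.

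What the objection does not remove is that the rule cannot be met at 9 or 10, and that at lower scores the text does not say how it would be established.

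**Conclusion.** The point holds as a minor one. The ceiling is certain from the text. The missing specification covers three items: the reference score, the time of the post-injection score, and how 24-hour duration is ascertained. Together they make this single complication liable to be under-counted.

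The amount cannot be derived from the documents. The illustration of about 0.1 to 0.7 of 1.7 expected events covers the ceiling alone. It rests on the assumed baseline distributions, on entry scores standing in for scores at injection, and on a literature rate that may use a different definition. No efficacy result depends on the point.

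**What to change.** 1. Add to the TEI CRF an NRS leg pain score immediately before each injection, including repeats.
2. Add one online item 24-48 hours after each injection, in the web questionnaire system already in use. It should ask for current NRS leg pain, whether leg pain is worse than before the injection, and whether this has lasted at least 24 hours.
3. Keep the definition of more than 1 point for pre-injection scores up to 8. For scores of 9-10, count patient-reported worsening that lasts at least 24 hours.
4. Report the two components separately and combined, per injection and per patient.

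The cost is a wording change, one CRF field and one short question for TEI patients. The reported rate may be higher. The criterion at 9-10 differs from that at lower scores, so the combined rate mixes two thresholds; separate reporting makes that visible.
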